5.3.1.2 General Exclusion Criteria

1. Subject with an indication for the index procedure of acute ST-segment elevation MI (STEMI).
2. Subject has a known hypersensitivity or contraindication to aspirin, heparin/bivalirudin, P2Y12 inhibitors (clopidogrel/prasugrel/ticagrelor), everolimus, cobalt, chromium, nickel, tungsten, acrylic and fluoro polymers or contrast sensitivity that cannot be adequately pre-medicated.
3. Subject with implantation of another drug-eluting stent (other than XIENCE) within 12 months prior to index procedure.
4. Subject has a known left ventricular ejection fraction (LVEF) $<30\%$.

**PROTOCOL ABT-CIP-10398 XIENCE 28 Global Study**

5. Subject judged by physician as inappropriate for discontinuation from P2Y12 inhibitor use at 1 month, due to another condition requiring chronic P2Y12 inhibitor use.
6. Subject with planned surgery or procedure necessitating discontinuation of P2Y12 inhibitor within 1 month following index procedure.
7. Subject with a current medical condition with a life expectancy of less than 12 months
8. Subject intends to participate in an investigational drug or device trial within 12 months following the index procedure.
9. Pregnant or nursing subjects and those who plan pregnancy in the period up to 1 year following index procedure. Female subjects of child-bearing potential must have a negative pregnancy test done within 7 days prior to the index procedure per site standard test.

Note: Female subjects of childbearing potential should be instructed to use safe contraception (e.g., intrauterine devices, hormonal contraceptives: contraceptive pills, implants, transdermal patches hormonal vaginal devices, injections with prolonged release.) It is accepted, in certain cases, to include subjects having a sterilised regular partner or subjects using a double barrier contraceptive method. However, this should be explicitly justified in special circumstances arising from the trial design, product characteristics and/or trial population.

10. Presence of other anatomic or comorbid conditions, or other medical, social, or psychological conditions that, in the investigator's opinion, could limit the subject's ability to participate in the clinical investigation or to comply with follow-up requirements, or impact the scientific soundness of the clinical investigation results.
11. Subject is currently participating in another clinical trial that has not yet completed its primary endpoint.

5.3.2 *Angiographic Eligibility Criteria*

All angiographic eligibility criteria are based on visual assessment.

5.3.2.1 *Angiographic Inclusion Criteria*

1. Up to three target lesions with a maximum of two target lesions per epicardial vessel.

Note:

- The definition of epicardial vessels means left anterior descending coronary artery (LAD), left circumflex coronary artery (LCX) and right coronary artery (RCA) and their branches. For example, the subject must not have >2 lesions requiring treatment within both the LAD and a diagonal branch in total.
 - If there are two target lesions within the same epicardial vessel, the two target lesions must be at least 15 mm apart per visual estimation; otherwise this is considered as a single target lesion.
2. Target lesion must be located in a native coronary artery with visually estimated reference vessel diameter between 2.25 mm and 4.25 mm.
 3. Exclusive use of XIENCE family of stent systems during the index procedure.

**PROTOCOL ABT-CIP-10398 XIENCE 28 Global Study**

4. Target lesion has been treated successfully, which is defined as achievement of a final in-stent residual diameter stenosis of <20% with final TIMI-3 flow assessed by online quantitative angiography or visual estimation, with no residual dissection NHLBI grade \geq type B, and no transient or sustained angiographic complications (e.g., distal embolization, side branch closure), no chest pain lasting > 5 minutes, and no ST segment elevation > 0.5mm or depression lasting > 5 minutes.

5.3.2.2 Angiographic Exclusion Criteria

1. Target lesion is in a left main location.
2. Target lesion is located within an arterial or saphenous vein graft.
3. Target lesion is restenotic from a previous stent implantation.
4. Target lesion is a chronic total occlusion (CTO, defined as lesion with TIMI flow 0 for at least 3 months).
5. Target lesion is implanted with overlapping stents, whether planned or for bailout.

Note: If there is more than one target lesion, all target lesions must satisfy the angiographic eligibility criteria. Non-target lesion (i.e., lesions that do not meet the angiographic criteria listed above) treatments are not allowed during the index procedure.

5.4 Subject Registration

Subject registration will occur after completion of successful index procedure (see “Angiographic Inclusion Criteria” above for definition of successful treatment of target lesion) but prior to discharge and up to 3 days post index procedure, upon confirmation of the following:

- Signed informed consent has been obtained;
- Subject has met all the inclusion and none of the exclusion criteria (including both general and angiographic criteria).

5.5 Subject Discontinuation

All registered subjects will be considered to have completed the trial upon trial completion of the 12-month follow-up.

Each registered subject shall remain in the trial until completion of the required follow-up period; however, a subject’s participation in any clinical trial is voluntary and the subject has the right to withdraw at any time without penalty or loss of benefit. Conceivable reasons for discontinuation may include, but not be limited to, the following:

- Subject death
- Subject voluntary withdrawal
- Subject withdrawal by physician as clinically-indicated
- Subject lost-to follow-up as described below

PROTOCOL ABT-CIP-10398 XIENCE 28 Global Study

- Subject’s follow-up is terminated according to **Section 3.4** Early termination of the Clinical Trial

The Sponsor must be notified of the reason(s) for subject discontinuation. The site will record this information on the eCRF and source documents and provide this information to the Sponsor. Investigators must also report this to their respective EC as defined by their institution’s procedure(s).

No additional follow-up will be required or data recorded from subjects once withdrawn from the trial, except for the status (deceased/alive).

However, if a subject withdraws from the trial due to problems related to the device safety or performance, the investigator shall ask for the subject's permission to follow his/her status/condition outside of the clinical trial.

Lost-to-Follow-up:

If the subject misses two consecutive scheduled follow up time points and the attempts at contacting the subject detailed below are unsuccessful, then the subject is considered lost-to follow-up. Site personnel shall make all reasonable efforts to locate and communicate with the subject (and document these efforts in the source documents), including the following, at each contact time point:

- A minimum of 2 telephone calls on different days over the specified follow-up windows to contact the subject should be recorded in the source documentation, including date, time and initials of site personnel trying to make contact.
- If these attempts are unsuccessful, a letter (certified if applicable) should be sent to the subject.
- If a subject misses one or more non-consecutive follow-up contact time points it will be considered a missed visit. The subject may then return for subsequent visits. If the subject misses two consecutive time points and the above-mentioned attempts at communicating with the subject are unsuccessful, the subject will be considered lost-to-follow-up.

Note: Telephone contact with general practitioner, non-trial cardiologist or relative without presence of subject or indirect documentation obtained via discharge letters will not be considered as subject contact.

Missed Visits:

- If a subject misses one or more non-consecutive follow-up contact time points, the visit will be considered a missed visit and subject is not lost-to-follow-up.
- If subject responds via written communication (including email correspondence), providing the protocol required data, these data will be collected in the case report form and the visit will not be considered a missed visit.

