**PROTOCOL ABT-CIP-10398 XIENCE 28 Global Study****1.0 INTRODUCTION****1.1 Trial Design**

XIENCE 28 Global Study is a prospective, single arm, multi-center, open label trial to further evaluate the safety of 1-month (as short as 28 days) dual antiplatelet therapy (DAPT) in subjects at high risk of bleeding (HBR) undergoing percutaneous coronary intervention (PCI) with the approved XIENCE family of coronary drug-eluting stents.

The XIENCE family stent systems include commercially approved⁵ XIENCE Xpedition Everolimus Eluting Coronary Stent System (EECSS), XIENCE Alpine EECSS, XIENCE PRO^X EECSS⁶, XIENCE Pro^A EECSS⁷, or XIENCE Sierra EECSS which are all manufactured by Abbott Vascular, Inc, Santa Clara, USA. The above listed XIENCE stents will hereinafter be called “XIENCE” in this trial.

[REDACTED] Trial population consists of non-complex HBR subjects with up to three native coronary artery lesions (a maximum of two lesions per epicardial vessel) with reference vessel diameter between 2.25 mm and 4.25 mm. Eligibility of P2Y12 receptor inhibitor discontinuation will be assessed at 1-month follow-up. Subjects who are free from myocardial infarction (modified ARC), repeat coronary revascularization, stroke, or stent thrombosis (ARC definite/probable) within 1 month (prior to 1-month visit but at least 28 days) after stenting AND have been compliant with 1-month DAPT without interruption of either aspirin and/or P2Y12 receptor inhibitor for > 7 consecutive days are considered as “1-month clear”, and will discontinue P2Y12 receptor inhibitor as early as 28 days and continued with aspirin monotherapy through 12-month follow-up.

All registered subjects will be followed at 1, 3, 6 and 12 months post index procedure.

The data collected from the XIENCE 28 Global Study will be compared with the historical control of non-complex HBR subjects treated with standard DAPT duration of up to 12 months from the XIENCE V USA Study⁸, which is a US post-approval study to evaluate the safety of XIENCE V EECSS in “all-comer” population under real-world setting.

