5.10 Trial Completion

A Trial Completion eCRF must be completed when:

- the subject is considered lost to follow-up per the above definition or
- the subject withdraws from the clinical trial or
- the investigator withdraws the subject from the clinical trial or
- the subject has died or
- upon clinical trial completion or
- sponsor termination of trial.

Sponsor must be notified of the reason for subject discontinuation. The site will provide this information on the eCRF. Investigators must also report this to their EC as defined by their institution's procedure. Subjects will not be replaced.

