**PROTOCOL ABT-CIP-10398 XIENCE 28 Global Study**

Clinical follow-up visits should be conducted by the investigator or trial personnel who have been trained to the protocol. At 1-month follow-up visit, the investigator or designee will assess whether the subject is “1-month clear” and eligible for P2Y12 inhibitor discontinuation per criteria defined in **Section 6.3.2**.

All registered subjects will be followed up through 12 months, regardless of eligibility to discontinue P2Y12 inhibitor.

The following information will be collected at each of the time points:

- Any adverse events
- Use and compliance of protocol required antiplatelet medication
- Details of any subsequent coronary interventions (e.g., repeat PCI or CABG).

Note that information obtained through indirect contacts with a subject’s healthcare provider or immediate family member will NOT be considered as a trial visit.

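### Physician-initiated withdrawal stops collection of non-fatal endpoint events even where consent stands; limit the vital-status-only rule to withdrawn consent

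*Protocol*

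**What the plan says.** Protocol 5.5 lists "Subject withdrawal by physician as clinically-indicated" among the reasons for discontinuation and does not define it. Protocol 5.10 requires the Trial Completion form when "the investigator withdraws the subject from the clinical trial". For every withdrawal, whoever starts it, 5.5 then says: "No additional follow-up will be required or data recorded from subjects once withdrawn from the trial, except for the status (deceased/alive".

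There is one exception. It applies "if a subject withdraws from the trial due to problems related to the device safety or performance", when the investigator asks for "permission to follow his/her status/condition outside of the clinical trial".

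Elsewhere the protocol commits to complete follow-up. Section 1.1 says "All registered subjects will be followed at 1, 3, 6 and 12 months post index procedure" and section 6.4 says "All registered subjects will be followed up through 12 months, regardless of eligibility to discontinue P2Y12 inhibitor". Section 6.3.2 keeps subjects who are not 1-month clear in follow-up to 12 months under treatment at the investigator's discretion.

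The primary endpoint (Protocol 4.1) is NACE from 1 to 6 months: death, MI, definite or probable stent thrombosis, stroke, or BARC 2-5 bleeding. SAP 2.5 uses multiple imputation for baseline data in the propensity score and otherwise analyses available data. SAP 2.9 adds a sensitivity analysis that imputes missing outcomes.

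**The concern.** Only withdrawn consent requires data collection to stop. A physician's decision to end participation does not, and nothing else in the trial needs it to. The stent is already in place at registration, and the protocol elsewhere follows subjects whose antiplatelet treatment departs from the plan. SAP 2.9 likewise defines 1-month-clear subjects who resume a P2Y12 inhibitor as non-compliant and removes them only in a sensitivity analysis, so it expects them to be observed.

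The single exception is tied to the device, whereas the trial's question is DAPT duration and Protocol 15.4 names shortened DAPT as the added risk. A subject withdrawn over bleeding concerns on the regimen would usually fall outside it.

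After withdrawal, one component of the composite stays visible and four do not. The trial is open label, so the withdrawing physician knows the regimen. A withdrawal made on clinical grounds may well be related to the risk of the events that are then lost. With missing outcomes excluded, such losses can lower the trial-arm rate entering a non-inferiority test on a difference.

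**Working it through.** **Inputs from the documents.** Margin 4.0 points and one-sided 0.05 (SAP 2.1.4); about 800 subjects in the 1-month DAPT arm and about 1,400 controls (SAP 1.5). The plan states no figure on withdrawals to reproduce.

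**Assumptions, not in the documents.** True 1 to 6 month NACE p = 10%; a fraction w of the arm withdrawn by the physician while event-free; total NACE risk q in those subjects; f = the part of q that is death.

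**Step 1, all post-withdrawal events unseen.** Excluding withdrawn subjects, the observed rate is (p − wq)/(1 − w).

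**Step 2, deaths recorded.** Suppose deaths count, withdrawn survivors are excluded, and f = q/2. The observed rate is (p − w(q − f))/(1 − w(1 − f)).

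| w | q | Step 1 rate | Shortfall (share of margin) | Step 2 rate | Shortfall (share of margin) |
|---|---|---|---|---|---|
| 1% | 30% | 0.0970/0.9900 = 9.80% | 0.20 (5%) | 0.0985/0.9915 = 9.93% | 0.07 (2%) |
| 2% | 40% | 0.0920/0.9800 = 9.39% | 0.61 (15%) | 0.0960/0.9840 = 9.76% | 0.24 (6%) |
| 3% | 50% | 0.0850/0.9700 = 8.76% | 1.24 (31%) | 0.0925/0.9775 = 9.46% | 0.54 (13%) |

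Step 2 is closer to the protocol, since vital status is kept. Step 1 is the upper figure for these inputs.

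**Step 3, when a shortfall arises.** In step 1 it needs q > p; if q = p there is no bias. In step 2 it needs (q − f)/(1 − f) > p, that is, a non-fatal event risk among withdrawn survivors above the arm's own rate. Below that, counting deaths while dropping survivors raises the observed rate slightly.

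**Step 4, effect on the test.** Set the true difference at the margin: control 10%, trial arm 14%, control fully observed, w = 2%, q = 30%. An unpooled normal approximation without stratification is used.

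- All unseen: rate (0.14 − 0.006)/0.98 = 13.67%, difference 3.67 points, n = 784. SE = √(0.1367 × 0.8633/784 + 0.10 × 0.90/1400) = 0.01466. False-pass probability Φ((0.04 − 0.0367)/0.01466 − 1.645) = about 7.8%, against a nominal 5%.
- Half recorded deaths: rate 0.137/0.983 = 13.94%, difference 3.94 points, SE 0.01472, probability about 5.5%.
- With control 15% (trial arm 19%), the same two cases give about 6.5% and 4.9%.

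The effect ranges from negligible to appreciable, depending on inputs the documents do not give.

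**The case against.** Much stands on the other side.

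- **Events before withdrawal are captured.** All adverse events are collected to 6 months (Protocol 7.3.1), and BARC type 2 includes overt bleeding that prompts evaluation (Appendix II). A reader might infer that subjects in clinical trouble can leave before their event counts. That is too broad: an overt bleed under work-up is generally already an endpoint event. The gap is a subject with no qualifying event who is withdrawn and then has a non-fatal one inside the window.
- **No flat contradiction.** One might read 5.5 as contradicting 6.4. The stress in 6.4 is on follow-up regardless of P2Y12 eligibility, and 5.5 itself qualifies its commitment by the right to withdraw. This is a tension. The qualifier does rest on the subject's right, so it does not explain physician withdrawal.
- **Direction.** It is tempting to say the rule favours non-inferiority. The test is on a difference, and the control's handling of withdrawals is not readable. Similar losses there would offset the effect.
- **Size.** A loss of 31% of the margin requires the most adverse inputs in the table and ignores recorded deaths. Neither the withdrawal fractions nor the risks have support in the documents.
- **SAP 2.9.** One might say its outcome imputation cannot repair the loss. The model is not visible and neighbouring text is redacted, so that cannot be shown. The readable text has no tipping-point or worst-case rule.
- **The device exception** could cover stent thrombosis or target-vessel ischaemia, so the gap there concerns mainly bleeding. The follow-up it allows is outside the trial, however, and does not restore endpoint data.

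None of this supplies a reason to stop collecting endpoint data when the physician withdraws a subject who still consents.

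**Conclusion.** The point holds as a weakness in the data-collection rule that is cheap to remove. Protocol 5.5 and 5.10 allow withdrawal by the physician without criteria, keep vital status alone, and do not distinguish this from withdrawn consent. Non-fatal NACE components can then be lost in a way related to prognosis, and the primary analysis excludes missing outcomes.

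The documents do not establish that bias will occur, how large it would be, or its net direction. The shortfalls of 0.20-1.24 points (all events unseen) and about 0.07-0.54 points (half recorded deaths) rest on an assumed 10% true rate, 1-3% withdrawn and 30-50% risk. If few subjects are withdrawn by physicians, or withdrawal is unrelated to risk, the effect is negligible.

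**What to change.** 1. In Protocol 5.5 and 5.10, restrict the vital-status-only rule to subjects who withdraw consent for follow-up.
2. State that a change in antiplatelet treatment or in clinical condition does not by itself end data collection. Such subjects stay in scheduled follow-up; section 6.4 already allows telephone contact. This concerns data collection only, not treatment.
3. Extend the permission request from device-related withdrawals to every withdrawal, within the trial and covering the NACE components.
4. If record review is to be used, align 5.5 and 6.4, which do not accept indirect contact or discharge letters as subject contact or a trial visit.
5. Add to SAP 2.9 a tipping-point analysis for outcomes missing after withdrawal.

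Cost: amendment and consent-form wording, possible re-consent of subjects already registered, a few extra contacts, and one further sensitivity analysis.

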2.5 Handling of Missing Data

The primary analysis will be evaluated after propensity score stratification. To handle missing data in propensity score building, multiple imputation methods will be performed for baseline characteristics to compute propensity scores from these datasets.

All other analyses will be based on available data with missing data excluded. Any unused or spurious data will be noted as appropriate in the final report.

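### The lost-to-follow-up rule requires no check on whether an unreachable subject has died or had an endpoint event

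*Protocol*

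**What the plan says.** - **When a subject is lost (Protocol 5.5).** The rule applies "If the subject misses two consecutive scheduled follow up time points and the attempts at contacting the subject detailed below are unsuccessful".
- **Effort required (Protocol 5.5).** "Site personnel shall make all reasonable efforts to locate and communicate with the subject", with the efforts documented at each contact time point. The named minimum is "A minimum of 2 telephone calls on different days over the specified follow-up windows to contact the subject"; if those fail, "a letter (certified if applicable) should be sent to the subject".
- **What counts as contact.** Under 5.5, "Telephone contact with general practitioner, non-trial cardiologist or relative without presence of subject or indirect documentation obtained via discharge letters will not be considered" as contact with the subject. Section 6.4 has a parallel note: "information obtained through indirect contacts with a subject" (through a care provider or close relative, as the sentence goes on to say) is not a trial visit.
- **Vital status (Protocol 5.5).** "No additional follow-up will be required or data recorded from subjects once withdrawn from the trial, except for the status (deceased/alive". This sentence concerns withdrawn subjects. Section 5.10 lists lost and withdrawn subjects as separate grounds for the Trial Completion form.
- **Analysis.** SAP 2.5 uses multiple imputation for the baseline characteristics that feed the propensity score, and then says: "All other analyses will be based on available data with missing data excluded". SAP 2.9 adds a sensitivity analysis that imputes missing primary outcomes and combines 10 datasets by Rubin's rule. The primary test (SAP 2.1.4) is one-sided at 0.05 with a 4.0-point margin. SAP 1.5 gives about 800 trial subjects and about 1,400 controls.

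**The concern.** All-cause death and stroke are components of NACE. A subject who has died, has had a disabling stroke or is in another hospital cannot answer a call or a letter, so the events being counted are themselves a reason for silence. The enrolled population makes this plausible: age 75 or over, prior stroke or dialysis each qualify a subject, and the 3-, 6- and 12-month contacts may all be by telephone.

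A death in month 2 leads to missed 3- and 6-month contacts. A death in month 4 leads to missed 6- and 12-month contacts. Either pair meets the definition of loss, and both deaths fall in the 1-to-6-month primary window. A site could carry out every named step and never learn of them. The outcome is then missing for a reason tied to its value, which no baseline covariate can be relied on to repair.

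**Working it through.** **1. Does any provision reach a silent subject?**

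| Provision | What it does | Does it require someone to look? |
|---|---|---|
| 5.5, effort | Open-ended duty to find and speak to the subject. Named minimum over two missed time points: 2 × 2 = 4 calls and 2 × 1 = 2 letters | No; it can be met without asking about vital status |
| 5.5 and 6.4 notes | Define contact and visit only; do not bar recording an event learned indirectly | No |
| 5.5, deceased/alive status | Stated for withdrawn subjects | Not stated for lost subjects |
| 6.5 | Asks for information on subjects treated in non-trial hospitals | In practice only once that treatment is known |
| 7.3.1 | SAEs reportable within 3 calendar days of site awareness, whatever the source | No; it starts at awareness |
| 5.10 | Trial Completion form when a subject has died | No; the death must be known |

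**2. The plan's own figures.** The rule carries no number, and no expected loss rate is visible. The sample size of about 800 cannot be reproduced because the assumed rates, power and attrition are redacted. An unstratified non-inferiority formula with equal true rates and 800 versus 1,400 subjects gives power of 98% at a 6% event rate, 91% at 10% and 81% at 15%, so 800 fits many hidden inputs.

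**3. Size of the understatement in the trial arm.** All inputs are assumed: p = NACE rate among those followed, l = share lost, k = risk among the lost relative to p, and every event among the lost unknown.

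Full-cohort rate = (1 − l)p + l·k·p, so the understatement is l(k − 1)p. With p = 10%:

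| l | k | Understatement | Share of 4.0-point margin |
|---|---|---|---|
| 1% | 2 | 0.01 × 1 × 10 = 0.1 points | 2.5% |
| 3% | 3 | 0.03 × 2 × 10 = 0.6 points | 15% |
| 5% | 5 | 0.05 × 4 × 10 = 2.0 points | 50% |

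In the middle row, 800 × 3% × 30% = 7.2 events are unseen. With k = 1 the understatement is zero.

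**4. Direction.** The shift in the estimated difference is the trial-arm understatement minus the control-arm understatement. With p = 10% and k = 3 in both arms, and 3% lost in the trial arm:

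- 0% lost in the control: 0.6 − 0 = 0.6 points in favour of non-inferiority.
- 3% lost in the control: 0.6 − 0.6 = 0.
- 5% lost in the control: 0.6 − 1.0 = −0.4 points, against non-inferiority.

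**5. Effect on the error rate, if loss occurs only in the trial arm.** Assume true rates of 12% and 8% (a difference exactly at the margin), complete-case analysis, and event rate q among a lost share d. The observed trial rate is (0.12 − d·q)/(1 − d). For d = 2% and q = 30% this is (0.12 − 0.006)/0.98 = 11.63%, with standard error √(0.1163 × 0.8837/784 + 0.08 × 0.92/1400) = 0.0136. The chance of declaring non-inferiority is then 8.5% instead of 5.0%. For d = 5% and q = 30% it is 17.3%. This is an unstratified approximation to the planned stratified Farrington-Manning test.

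**The case against.** The strongest reply is that the rule asks for more than a quick reading suggests, and that the notes on indirect sources are conservative.

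- **Effort.** The calls and letter are a floor under a wider duty, apply at each missed time point, and loss needs two misses in a row. This stands. But the stated aim is to reach the subject, so the duty can be discharged without learning whether the subject is alive.
- **Indirect sources.** A reader might infer that the protocol refuses information from doctors, relatives or discharge letters. It does not. The notes prevent such information from closing a visit; 7.3.1 makes any SAE the site learns of reportable. The gap is the missing duty to look.
- **Narrow path.** A subject who misses only month 6 is not lost, and events can be collected at month 12. That helps only if the subject can respond by then.
- **Analysis.** SAP 2.9 does address missing outcomes, but only as a sensitivity analysis. The visible text states no departure from missing at random and no tipping-point analysis.
- **Safety oversight.** A reader might infer that the DSMB is blind to deaths. Section 11.7.2 gives its chair or designee monthly adverse-event listings, so only deaths that no site learns of could escape it.
- **Visibility.** Text after the 6.4 visit schedule is redacted, and the eCRF and Monitoring Plan are not available. The point can be made only of the visible text.

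**Conclusion.** The point holds as a gap in data collection. In the visible text, no one has to establish whether an unreachable subject is alive or has had an endpoint event before that subject is classed as lost, and the primary analysis does not impute the outcome that then goes missing.

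The illustrated understatement of trial-arm NACE is 0.1–2.0 points, with a middle case of 0.6 points. Loss rate, relative risk and NACE rate are all assumed, so these figures show what the gap could do and are not an estimate for this trial.

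A reader might infer that the rule biases the trial towards non-inferiority. The documents do not support that without a condition: it requires loss to be informative and greater in the trial arm than in the XIENCE V USA control. How control-arm losses were ascertained is not described, and similar loss in both arms would largely cancel. The case for changing the rule does not depend on the direction: a death that one call to a relative could establish should not become a missing value.

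**What to change.** In Protocol 5.5, before a subject is classed as lost, and at the 6- and 12-month windows for anyone not reached, require a documented check of vital status and hospital admissions. It should use medical records, the general practitioner, the treating cardiologist and next of kin, plus a death register where local law and consent allow.

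State that this check is not a completed visit, but that any endpoint event it reveals is entered as an adverse event with source documents and sent to the CEC. Record deceased/alive status, with the date last known, for lost subjects as well as withdrawn ones.

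The cost is protocol, eCRF and consent wording and a few calls per unreached subject. The trial-arm event rate may come out slightly higher as a result.
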